Appendix 8. Eastern Cooperative Oncology Group (ECOG) Performance Status

ECOG Grade	Description	Karnofsky Score*
0	Fully active, able to carry on all pre-disease activities without restriction.	100
1	Restricted in physically strenuous activity but ambulatory and able to carry out work of a light or sedentary nature (light house work, office work).	80 or 90
2	Ambulatory and capable of all self-care but unable to carry out any work activities. Up and about more than 50% of waking hours.	60 or 70
3	Capable of only limited self-care, confined to bed or chair more than 50% of waking hours.	40 or 50
4	Completely disabled. Cannot carry on any self-care. Totally confined to bed or chair.	10, 20 or 30

* Karnofsky Score is provided for comparison purposes only. Please record ECOG Grade only.

Appendix 9. Local Laboratory Collection Requirements

Hematology Panel	
CBC (including Hemoglobin and Hematocrit)	
WBC with differential	
Platelets	
Neutrophils	
Liver Function Tests	
ALT	
AST	
Alkaline Phosphatase	
Total Serum Bilirubin *	
Direct bilirubin*	
Indirect bilirubin**	
Gamma-glutamyl transferase (GGT)**	
Total bile acids**	
Acetaminophen drug test and/or protein adduct levels**	
Blood Chemistry Panel	
Total Calcium	
Cholesterol (as clinically indicated)	
HDL (as clinically indicated)	
LDL (as clinically indicated)	
Sodium	
BUN or Urea	
Creatinine kinase** (as clinically indicated)	
Creatinine	
Albumin	
Potassium (as clinically indicated)	
Magnesium (as clinically indicated)	
Glucose	
HbA1C (as clinically indicated)	
Phosphorous	
Lipase	
Amylase	
Uric acid	
Coagulation Tests	
PT or INR	
PTT or aPTT	
Pregnancy Test	
Serum OR Urine (sensitivity of at least 25 mIU/mL)	

* Direct bilirubin must be collected if total serum bilirubin is $>1.5 \times$ ULN and for Hy's law determination, if appropriate.

** Collected for Hy's Law determination, if appropriate

Note: Hy's Law definition is defined in [Section 8.4.1](#)

PF-05208763

B1871039

Final Protocol Amendment 1, 07 September 2017

CCI

PF-05208763

B1871039

Final Protocol Amendment 1, 07 September 2017

CCI

CCI

Appendix 11. European LeukemiaNet Guidelines for Response in CML

Definitions of Hematologic, Cytogenetic, and Molecular Response²⁶

Response by Type	Definitions
Hematologic Complete (CHR)	WBC <10 x 10 ⁹ /L Peripheral Blood Basophils <5% No Peripheral Blood myelocytes, promyelocytes, myeloblasts in the differential Platelet count <450 x 10 ⁹ /L Spleen nonpalpable
Cytogenetic * Complete (CCyR) Partial (PCyR) Minor (mCyR) Minimal (minCyR) None (noCyR)	No Ph+ metaphases 1% to 35% Ph+ metaphases 36% to 65% Ph+ metaphases 66% to 95% Ph+ metaphases >95% Ph+ metaphases
Molecular Deep Molecular Response (MR4, MR4.5)	MR4= either (i) detectable disease with <0.01% BCR-ABL1 ^{IS} or (ii) undetectable disease in cDNA with >10 000 ABL1 transcripts MR4.5 =either (i) detectable disease with < 0.0032% BCR-ABL1 ^{IS} or (ii) undetectable disease in cDNA with >32,000 ABL1 transcripts in the same volume of cDNA used to test for BCR-ABL1.
Major (MMR)	Ratio of BCR-ABL ^{IS} ≤0.1%**.

Abbreviations: CHR, complete hematologic response; CCyR, complete cytogenetic response, PCyR, partial cytogenetic response; Ph+, Philadelphia Chromosome positive; MCyR, major cytogenetic response; mCyR, minor cytogenetic response; minCyR, minimal cytogenetic response; noCyR, no cytogenetic response; MR4, MR4.5, deep molecular response; MMR, major molecular response;.

*If bone marrow metaphases cannot be obtained or evaluated by chromosome banding analysis, the definition of CCyR (defined as <1% for FISH) may be based on interphase FISH of blood cells, provided that it is performed with Dual-Color Dual-Fusion or Dual-Fusion FISH probes and at least 200 nuclei are scored. PCyR and CCyR are counted together and reported as MCyR.

**With >=5,000 ABL1 transcripts.

Definitions of Hematologic Response for AP and BP CML^{29*}

CHR**	WBC \leq institutional upper limit of normal (ULN) ANC \geq 1.0 x 10^9 /L Platelet count \geq 100 x 10^9 /L BM Blasts \leq 5% *** No peripheral blood blasts or promyelocytes; Peripheral blood myelocytes + metamyelocytes $<$ 5%; Basophils in peripheral blood $<$ 5%* No evidence of extramedullary involvement
-------	--

*The maximum % of basophils in peripheral blood was modified from < 2 to $< 5\%$ for a less restrictive constraint and alignment with the CHR criteria for CP CML patients according to ELN guidelines.

1. AMENDMENTS FROM PREVIOUS VERSION(S)

The SAP version 3.0 amended SAP v2.0 dated September 28, 2017. The main changes are COVID-19 related and additional exploratory analyses which included:

- Impact on analyses from COVID-19;
- Additional analyses of deep molecular response.

The SAP version 2.0 amended the original SAP v1.0 dated March 18, 2014. The main changes to align with protocol amendment #1 included:

- Change the primary endpoint analysis to (1) require maintenance of baseline response for at least one year on-treatment for patients with complete cytogenetic response (CCyR) at baseline, (2) require confirmation of initial on-treatment cytogenetic response (in the absence of major molecular response [MMR]) by a second consecutive response at least 28 days apart, and (3) be based on treated patients with a valid baseline efficacy assessment;
- Addition of secondary endpoints duration of CCyR and duration of MMR;
- Include imputation of cytogenetic response from molecular monitoring data if cytogenetics is not performed;
- Update appendices for molecular, cytogenetic and hematologic response criteria;
- Update required number of 4th line patients from at least 75 to 45.

2. INTRODUCTION

On September 4, 2012, bosutinib was approved by the US Food and Drug Administration (FDA) for the treatment of adult patients with chronic (CP), accelerated (AP), or blast phase (BP) Philadelphia chromosome positive (Ph+) Chronic myelogenous leukemia (CML) with resistance or intolerance to prior therapy (United States Prescribing Information BOSULIF®). More recently, on March 27, 2013, the European Medicines Agency (EMA) granted conditional marketing authorization in the European Union (EU), for the treatment of adult patients with CP, AP and BP Ph+ CML previously treated with one or more tyrosine kinase inhibitors (TKIs) and for whom imatinib, nilotinib and dasatinib are not considered appropriate treatment options (EMA Summary of Product Characteristics).

Furthermore, in 5%–10% of patients with chronic myelogenous leukemia (CML), the Philadelphia chromosome (Ph) is not identified despite the presence of the associated BCR-ABL molecular abnormality (Ph-negative, BCR-ABL-positive CML) because of submicroscopic rearrangements. Regardless, the presence of the BCR-ABL fusion gene will translate into a BCR-ABL fusion protein with dysregulated tyrosine kinase activity. Therefore, a TKI targeting BCR-ABL is also an effective treatment also for Ph negative CML patients. The FDA and EMA approvals were granted based on the results obtained from the single arm, Phase 1/2 study (3160A4-200-WW, “Study-200”) in adult patients with Ph+

leukemias who had failed prior TKI therapy, and with the support of the safety results obtained from the Phase 3 study (3160A4-3000-WW) comparing bosutinib with imatinib in newly diagnosed CP Ph+ CML patients. In addition, the EMA was provided with descriptive narrative information from the bosutinib compassionate use program in patients with Ph+ CML who had received at least one prior TKI treatment and had progressed or were intolerant, and otherwise not considered suitable for other TKI therapy, as well as efficacy and safety analyses from a subset of Study-200 patients whose disease had failed prior imatinib and/or dasatinib or nilotinib and were contraindicated for treatment with dasatinib or nilotinib, as well as 4th-line CML patients on the study.

The purpose of this phase 4 study is to fulfill the post-authorization commitment made by Pfizer to the EMA in providing additional safety and efficacy data in approximately 150 Ph+ CML patients with high unmet medical need, including at least 75 CP, AP or BP patients in the 4th or later line treatment setting (ie, after treatment with at least 3 other TKIs). The EMA conditional approval requires completion of this post-authorization study in order to convert the conditional approval to a full marketing authorization approval.

This study was initiated in November 2014 and the original target projection was 75 patients in each cohort. However, the 4th line cohort has not met its planned targeted enrollment objective; whereas, the 2nd/3rd-line cohort has overenrolled (n=106). Therefore, Pfizer decided based on CHMP feedback to stop recruitment after at least 45 patients have been enrolled in the 4th line cohort. It was further agreed, there are sufficient numbers of patients in each cohort to perform an informative descriptive analysis of the safety and efficacy and safety of bosutinib.

2.1. Study Design

This is a single-arm, open-label, non-randomized, multi-center Phase 4 study to evaluate bosutinib (Bosulif®) in patients with CP/AP/BP Ph+ CML whose disease has failed prior treatment with commercially available TKIs due to drug resistance or intolerance, or are otherwise contraindicated for treatment with commercially available TKIs such as imatinib, dasatinib, or nilotinib (ie, presence of a BCR-ABL mutation or medical condition making commercially available TKIs unsuitable for a patient). Patients will receive bosutinib for at least 4 years from the time of first dose, unless disease progression, unacceptable toxicity, patient withdrawal of consent, death or Sponsor discontinuation of study. Patients discontinuing bosutinib prior to completing at least 4 years of therapy will be followed for survival until they complete at least 4 years of follow-up from the time of first dose. Patients completing at least 4 years of bosutinib with continued benefit may be switched to commercially available therapy at that time.

Patients are allocated to the cohort based on the derived assignment from the baseline disease stage and prior TKI therapy. Patients are either:

- CP Ph+ CML second line (CP2L) resistant or intolerant to imatinib, dasatinib, or nilotinib;
- CP Ph+ CML third line (CP3L) resistant or intolerant to imatinib and dasatinib, imatinib and nilotinib, or dasatinib and nilotinib;

- CP Ph+ CML fourth or later line (CP4L) resistant or intolerant to imatinib, dasatinib, and nilotinib;
- AP Ph+ CML second line (AP2L) resistant or intolerant to imatinib, dasatinib, or nilotinib;
- AP Ph+ CML third line (AP3L) resistant or intolerant to imatinib and dasatinib, imatinib and nilotinib, or dasatinib and nilotinib;
- AP Ph+ CML fourth or later line (AP4L) resistant or intolerant to imatinib, dasatinib, and nilotinib;
- BP Ph+ CML second line (BP2L) resistant or intolerant to imatinib, dasatinib, or nilotinib;
- BP Ph+ CML third line (BP3L) resistant or intolerant to imatinib and dasatinib, imatinib and nilotinib, or dasatinib and nilotinib;
- BP Ph+ CML fourth or later line (BP4L) resistant or intolerant to imatinib, dasatinib, and nilotinib, or
- Ph- CML.

Patients will be summarized based on these cohorts or a combination of these cohorts (eg, CP with 1 or 2 prior lines of TKI therapy includes CP2L and CP3L, CP total includes CP2L, CP3L, and CP4L). AP (AP2L, AP3L, AP4L) and BP (BP2L, BP3L, BP4L) patients combined are known as advanced patients. All Ph- CML patients will be summarized separately. Patients who were both resistant and intolerant to the prior TKI or neither will be considered intolerant to that TKI for analysis purposes.

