6.1. Screening

Screening can be accomplished over one or multiple visits over a 4-week period (30 days). Stage of disease is defined as the worst phase of CML experienced by the patient, regardless of disease status at the time of study entry. For example, a patient whose disease is in CP at study entry, but who had been previously diagnosed in AP, will be classified as AP CML. Refer to [Appendix 7](#) for specific criteria for CP, AP and BP phases of disease.

Prior cancer history, including CML and any other cancer will be collected. All treatments received by the patient for CML (CP, AP, and BP), including dates of administration, dose(s), best response and tolerability (including specific intolerance(s) to each therapy) will be collected from the time of original diagnosis of CML. Any additionally diagnosed malignancies will also be recorded at screening.

All relevant medical history and treatment received by the patient within 30 days before administration of bosutinib will be recorded on the patient's CRF, including the name of the procedure or drug and other related information.

The following procedures should be conducted as part of the baseline screening:

- Signature of informed consent document (ICD);
- Review of patient's eligibility (i.e., protocol inclusion/exclusion criteria);
- Cytogenetic confirmation of Ph+ chromosome (or BCR-ABL1+ if Ph-) CML diagnosis and phase. Acceptable documentation includes results from primary CML diagnosis or results following discontinuation/ failure of prior CML therapy. Either traditional cytogenetics for the Ph+ chromosome or fluorescence in situ hybridization (FISH) for the BCR-ABL juxtaposition or PCR for BCR-ABL transcript quantification are acceptable for the diagnosis of CML;
- Medical history;

- Complete physical examination to include vital signs (sitting or supine blood pressure, heart rate, and height and weight);
- Smoking status at screening; (Note: the use of TKIs could lead to cumulative long-term cardiovascular disease therefore information of other risk cardiovascular factors like smoking status will be collected for this study);
- Extramedullary disease assessment (including assessment of liver, spleen and lymph nodes by physical examination as well as other potential sites of extramedullary involvement);
- ECOG performance status ([Appendix 8](#));
- Electrocardiogram (ECG);

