Appendix 7. Criteria to Identify Phase of CML

Phase ^{a, 27,28}	Findings
Blast Phase	
$\geq 30\%$ Blasts in blood or bone marrow Extramedullary Blasts proliferation, apart from spleen
 
If either of these 2 criteria is present, the patient is classified as Blast Phase regardless of other criteria.

Accelerated Phase	
15-29% Blasts in blood or bone marrow OR $>30\%$ Blasts + Promyelocytes (with Blasts $<30\%$) in blood or bone marrow OR $\geq 20\%$ Basophils in blood or bone marrow OR Persistent platelets $<100 \times 10^9/L$ (not related to therapy)OR
 
Clonal chromosomal abnormalities in Ph+ cells (CCA/Ph +), major route, on treatment

Chronic Phase	
$<15\%$ Blasts $<20\%$ Basophils $\leq 30\%$ Blasts + Promyelocytes (with Blasts $<15\%$) in blood or bone marrow
 
AND Platelets $\geq 100 \times 10^9/L$ (unless related to therapy)
 
AND No Extramedullary Blasts (except spleen)

^a Observance of any one criterion in the worse disease phase achieves that phase as the diagnosis (e.g., 20% basophils alone elevates the diagnosis from CP to AP).

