6. ENDPOINTS AND COVARIATES

In general, the baseline value will be defined as the last non-missing value prior to first dose, unless specifically stated otherwise. Assessments performed on Week 1 day 1 will be assumed to be pre-dose per the schedule of activities in the Protocol.

An on-treatment evaluation is defined as any evaluation done during bosutinib therapy or within 28 days of last dose.

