6.3. Other Endpoints

6.3.1. Demographic, Medical History, and Baseline Characteristics

Demographic and baseline variables will include the following:

- Age ([the date of the signing of the informed consent form – the birth date]/365.25 in integer years), sex, race, height, and weight;
- Medical history;
- Cancer history (prior cancer history including CML and initial and current CML disease stage);
- Prior cancer therapies (interferon, imatinib, dasatinib, and nilotinib) and resistance/intolerance status for prior TKIs;
- Eastern Cooperative Oncology Group (ECOG) performance status.

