Appendix 1. CRITERIA TO IDENTIFY PHASE OF CML

Phase ^a	Findings
Blast Phase	
$\geq 30\%$ Blasts in blood or bone marrow Extramedullary Blasts proliferation, apart from spleen
 
If either of these 2 criteria is present, the patient is classified as Blast Phase regardless of other criteria.

Accelerated Phase	
$15\text{--}29\%$ Blasts in blood or bone marrow or $>30\%$ Blasts + Promyelocytes (with Blasts $<30\%$) in blood or bone marrow OR $\geq 20\%$ Basophils in blood OR Persistent platelets $<100 \times 10^9/L$ (not related to therapy) OR Clonal chromosomal abnormalities in Ph+ cells (CCA/Ph +), major route, on treatment

Chronic Phase	
$<15\%$ Blasts $<20\%$ Basophils $\leq 30\%$ Blasts + Promyelocytes (with Blasts $<15\%$) in blood or bone marrow
 
AND Platelets $\geq 100 \times 10^9/L$ (unless related to therapy)
 
AND No Extramedullary Blasts (except spleen)

^a Observance of any one criterion in the worse disease phase achieves that phase as the diagnosis (eg, 20% basophils alone elevates the diagnosis from CP to AP).

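### SAP 2.1 assigns cohorts from an undefined baseline disease stage while Protocol 6.1 uses the worst phase ever reached; stage selects the primary endpoint, so the two need reconciling

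*SAP*

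**What the plan says.** The cohort rule in SAP 2.1 reads: "Patients are allocated to the cohort based on the derived assignment from the baseline disease stage and prior TKI therapy". The SAP does not say what disease stage at baseline means. Its general rule in Section 6 is that "the baseline value will be defined as the last non-missing value prior to first dose, unless specifically stated otherwise", and no other rule is given for stage. The baseline variables in SAP 6.3.1 include "Cancer history (prior cancer history including CML and initial and current CML disease stage"; worst phase is not among them.

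Protocol 6.1 is explicit: "Stage of disease is defined as the worst phase of CML experienced by the patient, regardless of disease status at the time of study entry". It adds an example: "a patient whose disease is in CP at study entry, but who had been previously diagnosed in AP, will be classified as AP CML".

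The criteria for AP also differ in one cell. At a level of 20% or more, Protocol Appendix 7 counts "Basophils in blood or bone marrow". The matching line in SAP Appendix 1 stops at "Basophils in blood".

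SAP 8.2.1 then attaches the primary endpoint to the stage: confirmed MCyR by Week 52 for CP (second and third line combined, fourth and later line separately), and confirmed OHR by Week 52 for AP and for BP. Under SAP 6.1, holding a baseline response counts as response after at least 5 weeks for hematologic response and at least 52 weeks for cytogenetic response.

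**The concern.** The assignment rule decides which patients enter each of the primary analyses and which endpoint each is judged on. If the SAP is programmed by its own default, a patient who had AP or BP and returned to CP before entry goes into an MCyR analysis. Under the protocol the same patient goes into an OHR analysis. Stage also selects the complete hematologic response (CHR) criteria in SAP Appendix 2 and the progression criteria for PFS in SAP 6.1.

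The study tests no hypothesis. Its product is a set of response rates with exact confidence intervals, so who is counted in each rate is the result itself. The study is open-label, and SAP 8.2.2 records that all patients had passed Week 52 before March 2020. A rule left open in the SAP could therefore be settled with outcomes already visible.

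A second question remains whichever document is followed to the letter. Once worst phase is the rule, the AP and BP groups can contain patients who enter in CP or already in hematologic response. For them, OHR can be met without any improvement.

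**Working it through.** **1. The plan's own figure.** The only precision figure is in Protocol 9.1, a standard deviation of at most 0.075 with 45 patients. √(0.5 × 0.5 / 45) = 0.0745, so it reproduces. It does not bear on stage assignment, and no AP or BP sample size is given.

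**2. One patient under both texts.** Take a patient diagnosed in CP, later in AP, and back in CP at screening.

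| Source | Stage | Primary endpoint |
|---|---|---|
| Protocol 6.1 (worst phase) | AP | confirmed OHR |
| SAP 2.1 read with the SAP 6 default | CP | confirmed MCyR |
| SAP 6.3.1 fields, initial and current | CP and CP | the AP episode is not visible |

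The last row matters for the fix. Initial and current stage alone cannot recover worst phase. Protocol 6.1 does collect the CML history and treatments from original diagnosis, so the information exists elsewhere.

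**3. The two bars.** Suppose this patient does not change on treatment.

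- As AP: if the CHR criteria for advanced disease are met at baseline and held for at least 5 weeks, the patient is an OHR responder.
- As CP: without a baseline major cytogenetic response the patient is a non-responder. With baseline partial response, complete response must be reached. With baseline complete response, it must be held for at least 52 weeks.

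OHR also includes return to chronic phase, which neither Protocol Appendix 11 nor SAP Appendix 2 defines. SAP 6.1 points to SAP Appendices 2 and 1 for response definitions, so the CP row of Appendix 1 is the only SAP text from which return to CP could be derived. Treating CP at entry as a baseline return to CP is therefore plausible but inferred. The route through baseline CHR needs no such inference.

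**4. Basophils.** The two appendices differ only for a patient with at least 20% basophils in marrow, less than 20% in blood, and no other AP or BP criterion. The protocol makes this patient AP; the SAP does not. Whether the SAP makes the patient CP depends on whether the blood-or-marrow wording in its CP row also governs the basophil limit. If it does, the patient fits no phase.

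**5. Size, with assumed numbers throughout.** Let x of n advanced-phase patients respond, and add k patients who entered in CP or in hematologic response. If all k count as responders, the rate becomes (x + k)/(n + k).

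| Assumed start | k | Result |
|---|---|---|
| 6/12 = 50.0% | 2 | 8/14 = 57.1% |
| 4/8 = 50.0% | 1 | 5/9 = 55.6% |
| 10/20 = 50.0% | 1 | 11/21 = 52.4% |
| 5/10 = 50.0% | 1, 3, 5 | 54.5%, 61.5%, 66.7% |
| 8/15 = 53.3% | 1, 3, 5 | 56.2%, 61.1%, 65.0% |

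These are the upper case. For 6/12 with k = 2, one responder among the two gives 7/14 = 50.0%, and none gives 6/14 = 42.9%. The exact 95% interval for 6/12 is about 21% to 79%, far wider than the shift.

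In CP the effect is small. With an assumed 50/100, adding two non-responders gives 50/102 = 49.0%, a change of 1 point.

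**The case against.** A reader might infer that the SAP has replaced the worst-phase rule with status at entry. The documents do not support that. The SAP never rejects the protocol rule. The protocol defines the term stage of disease in its screening section, so a stage recorded at baseline could simply be the protocol's stage. The SAP speaks of a derived assignment, which suggests more than looking up a last value. Its default for baseline is introduced as general and allows exceptions, and it uses a different term, current stage, for status at entry. Protocol Section 9 also promises an amendment for any major change to the primary endpoint or its analysis, and Amendment 1 keeps the worst-phase rule. All of this stands. The point is an undefined term whose default meaning conflicts with the protocol, not an express contrary rule.

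A reader might also infer that the SAP wording inflates OHR. It is the other way round. The upward shift illustrated above comes from the protocol's worst-phase rule combined with the 5-week maintenance rule; reading the SAP as status at entry would take these patients out of OHR. Aligning the SAP with the protocol therefore does not remove the shift. Only a supportive table shows it.

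It is also fair that no count of AP or BP patients, or of such patients entering in CP, is given; that no decision rule depends on these rates; and that the basophil difference is marginal. What survives is that two current texts, read as written, can send one patient to different primary endpoints.

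**Conclusion.** The passages diverge and should be reconciled. Under the SAP's default definition of baseline, cohort stage is status at entry; under Protocol 6.1 it is the worst phase ever reached. Because SAP 8.2.1 ties the primary endpoint to stage, the difference can move a patient between MCyR and OHR. This rests on applying the SAP's general baseline rule to a term it leaves undefined. The basophil mismatch is certain on the text but can affect only a few patients.

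Separately, and as a consequence of the protocol's own rule, a patient with AP or BP history who enters in CP or in hematologic response can count as an OHR responder by holding that status for 5 weeks. For return to CP, this also assumes that CP at entry counts as a baseline response.

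The size cannot be derived from the documents. A move from 50% to 57% assumes 12 patients, 6 responders and two added patients who both respond. It shows that small groups are sensitive to assignment. It is not an estimate of bias in this study.

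**What to change.** 1. In SAP 2.1, cite Protocol 6.1 as the rule for cohort stage, and state that it is derived from the full CML history collected at screening, not only from initial and current stage. If status at entry is what is intended, amend the protocol instead.
2. Make the AP basophil criterion the same in Protocol Appendix 7 and SAP Appendix 1.
3. Add one supportive table: the number of AP and BP patients who entered in CP or already in hematologic response, and OHR for AP and for BP with and without them. A footnote should give the criteria used for return to CP. SAP 8.2.2 already plans analyses without baseline responders for MMR and MCyR, but not for OHR.

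The cost is SAP wording and one table. No new data collection is needed, although deriving worst phase means using the disease history as well as the two stage fields.
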